3.3. Randomization Scheme

The subject randomization codes will be designed by statisticians independent of the study. During the trial, enrollment numbers will be assigned according to the randomization schedule, and subjects in each dose group will be randomly assigned to receive BGT-002 or placebo.

The randomization schedule will be prepared by the randomization statistician before the start of the study. Screened eligible subjects will be assigned with subject numbers in ascending order of screening number, and the investigator will ensure that the corresponding drug is given to the subjects according to the numbers.

Sponsor: Burgeon Therapeutics Co., Ltd.

Statistical Analysis Plan
Protocol No.: BGT-002-004

Version/Date: V1.0/2024-04-16

3.4. Blinding

The study drug and placebo will be provided by the sponsor or its designated unit to ensure that the shape and weight of the placebo are similar to those of the study drug. The study drug and placebo in each treatment group will be blinded by the unit designated by the sponsor, and the statisticians will randomize the subjects into the study drug group or placebo group.

3.5. Unblinding

Emergency unblinding: When it is really necessary to unblind in an emergency, the Principal Investigator (PI) and Sponsor should be consulted. The authorized investigator can use the emergency letter to unblind with the consent of the PI and Sponsor.

Unblinding regulations: This trial will involve one unblinding. After the database is locked, the unblinding will be carried out with the consent of the study site and the Sponsor, and relevant personnel who keep the blinding codes will submit the randomization information of the trial to the statistical department for statistical analysis.

4. Criteria for Evaluation

4.1. Tolerability and Safety Evaluation Indicators

The safety and tolerability of BGT-002 in subjects after administration will be evaluated.

Adverse events (AEs) throughout the study will be evaluated and graded according to CTCAE 5.0.

The indicators will include symptoms and physical examination, clinical laboratory tests (hematology, coagulation function, blood chemistry and urinalysis), vital signs (blood pressure, pulse, respiration and body temperature) and 12-lead ECG.

C-QTc study: To investigate the effect of BGT-002 in 75 mg, 100 mg, 150 mg and 200 mg (alternative) dose groups on QT/QTc interval in subjects, a C-QTc study will be conducted for 36-48 subjects on D1 and D28.

4.2. PK Variables

Evaluation of PK parameters for BGT-002 and its metabolites (if applicable) will include:

Evaluation of PK parameters on Day 1 (D1): C_{max}, T_{max}, AUC_{0-24h}, etc.;

Evaluation of steady-state PK parameters (D28): C_{max,ss}, T_{max,ss}, AUC_{0-24h,ss}, CL_{ss}/F, C_{min,ss},

Rac, etc.

4.3. PD and Exploratory Evaluation Indicators

Primary Efficacy Variables:

Changes from baseline in ALT, AST, BMI and blood lipid levels at Week 4 and Week 8;

Change from baseline in liver fat content measured by MRI-PDFF at Week 4 and Week 8;

Proportion of subjects with a relative reduction of at least 30% in liver fat content measured by MRI-PDFF at Week 4 and Week 8;

Secondary Efficacy Variables:

Changes from baseline in CAP and LSM at Week 4 and Week 8;

Exploratory Variables:

Changes from baseline in biomarkers (CK18, FGF21, IP10, hsCRP, TIMP1, β -HB) at Week 4 and Week 8.

5. Data Sets Analyzed

Full Analysis Set (FAS): Randomized subjects who received at least 1 dose of the study drug.

Safety Set (SS): Randomized subjects who received at least 1 dose of the study drug with safety data available.

Pharmacokinetics Set (PKS): Randomized subjects who received at least 1 dose of the study drug with at least one evaluable PK concentration data. The inclusion of subjects in the PKS will be determined on a case-by-case basis at the data verification meeting.

Pharmacodynamics Set (PDS): Randomized subjects who received at least 1 dose of the study drug with at least one valid PD evaluation data. The inclusion of subjects in the PDS will be determined on a case-by-case basis at the data verification meeting.

6. Statistical Methods

6.1. General Principles

Statistical analysis will be completed using SAS 9.4 or above, and PK parameters will be calculated using WinNonlin 8.3 or above. Measurement data will be statistically described using the number of subjects, mean, standard deviation, median, quartiles, minimum and

maximum. For some measurement data, coefficient of variation, geometric mean and geometric coefficient of variation will also be calculated; count data and ranked data will be statistically described using the frequency and percentage of each category or rank. Unless otherwise specified, missing values will not be included in the calculation of percentage.

In the statistical analysis, subjects who receive the placebo will be combined as a placebo group for analysis.

6.2. Data Processing Methods

6.2.1. Rounding of Data

Measurement data: The minimum and maximum will be rounded to the same decimal place as the original data, the mean, geometric mean, median and quartiles will be rounded to one more decimal place than the original data (in case of inconsistency, the most decimal places will be taken), the standard deviation will be rounded to 2 more decimal places than the original data, with a maximum of four decimal places retained, and the coefficient of variation, geometric coefficient of variation and percentage change will be rounded to 2 decimal places.

Count data: Percentages will be uniformly rounded to one decimal place and marked with a percentage sign, such as x (x.x%). The brackets are all brackets in English form. If the percentage of an item in a table is 100%, it will be marked as x (100%). If the frequency of an item in a table is 0, it will be marked as 0. Unless otherwise specified in the table, the number of missing subjects will not be included in the denominator for percentage calculation.

The confidence interval (CI) will be rounded to the same number of decimal places as its point estimate.

For P values, the P value 6.4 format in SAS will be used.

6.2.2. Handling of Missing Data

All data will be based on available observational data, and missing data will not be imputed; in case of outliers, the handling method will be determined through discussion at the Data Review Meeting.

6.2.3. Handling of Other Abnormal Data

In case of a vacancy, "missing" will noted in the shift table according to the statistical

tabulation rules. However, the raw data will be presented in the listings and no further processing of the data will be considered.

6.3. Study Subjects

6.3.1. Disposition of Subjects

- The flow chart for the disposition of subjects will be prepared
- The subjects screened, enrolled, screen failed/excluded, and reasons for screen failure/exclusion will be described in frequency and percentage
- The final status of enrolled subjects, major protocol deviations and each analysis data set were described by dose group in frequency and percentage
- The subjects screen failed/excluded, final status of enrolled subjects, early withdrawal subjects, protocol deviations and subjects excluded from the analysis set will be listed

6.3.2. Demographic and Other Baseline Characteristics

Based on FAS, the demographics and baseline characteristics of subjects will be summarized and analyzed by dose group, with the latest examination result before the first dose as the baseline.

- Demographics will include age, gender, ethnicity, baseline height, weight and BMI
- Baseline characteristics will include past/present medical history, smoking history, drinking history, allergic history, blood donation/transfusion history, clinical trial history, HbA1c, creatinine clearance rate, infectious disease screening, alcohol breath test, urine drug screen, ANA test, thyroid function, chest X-ray, abdominal B-scan ultrasonography (liver, gallbladder, spleen, pancreas and both kidneys), prior medications and prior non-drug therapies
 - Medication history will be coded using ATC/DDD (Version 2023 or above)
- Medical history and non-drug therapy history will be coded using MedDRA (Version 26.0 or above)
- Demographics, past/present medical history, smoking history, drinking history, allergic history, blood donation/transfusion history, clinical trial history, HbA1c, creatinine clearance rate, infectious disease screening, alcohol breath test, urine drug screen, ANA test,

thyroid function, chest X-ray, abdominal B-scan ultrasonography, prior medications and prior non-drug therapies will be listed

6.3.3. Extent of Exposure

Based on FAS, the total number of study drug exposures, actual cumulative dose and treatment compliance of subjects will be summarized and analyzed by dose group.

- Total number of exposures = total number of study drug administrations
- Planned cumulative dose (mg) = total number of planned exposures × planned dose
- Actual cumulative dose (mg) = Sum of actual dose administered each time
- Treatment compliance (%) = (actual cumulative dose/planned cumulative dose) ×
 100%
- Treatment compliance will be statistically classified as <80%, 80%-120% and >120%
- Study drug administrations will be listed

6.3.4. Concomitant Medication/Non-Medication Therapy

Concomitant medications and concomitant non-drug therapies of subjects will be summarized and analyzed by dose group based on FAS.

- Concomitant medications will be coded using ATC/DDD (Version 2023 or above)
- Concomitant non-drug therapies will be coded using MedDRA (Version 26.0 or above)
- Concomitant medications and concomitant non-drug therapies will be listed

6.4. Analysis of Efficacy

6.4.1. Analysis of Plasma Concentrations

Based on PKS, the plasma concentrations of BGT-002 and its metabolites in subjects will be descriptively analyzed by dose group, visit and planned blood collection time point, with the number of subjects, mean, standard deviation, geometric mean, median, quartiles, maximum, minimum, coefficient of variation, and geometric coefficient of variation listed.

• When the plasma concentration is descriptively analyzed by visit and planned blood collection time point, plasma concentration values below the quantification limit (BQL) will

be treated as missing values, and concentration data beyond the window will not be included in the descriptive analysis of plasma concentration at the time point

- The mean plasma concentration (c)-time (t) curve (plasma concentration-time curve) will be plotted according to the planned blood collection time, and the individual plasma concentration-time curve will be plotted according to the actual blood collection time (actual blood collection time = actual blood collection date and time-actual administration date and time; the actual blood collection time before dosing is 0 h). For plasma concentration values below the quantification limit (BQL), those before reaching C_{max} will be treated as 0, while those after reaching C_{max} will be treated as missing values
- PK blood collection points: 0 h pre-dose (within 60 min pre-dose), 10 min (±0.5 min), 20 min (±0.5 min), 40 min (±1 min), 1 h (±1 min), 1.5 h (±1.5 min), 2 h (±1.5 min), 3 h (±3 min), 4 h (±3 min), 6 h (±6 min), 8 h (±6 min), 12 h (±12 min), and 24 h (±36 min) post-dose on D1; within 60 min pre-dose on D8, D15, D22, D26, and D27; 0 h pre-dose (within 60 min before dosing), 10 min (±0.5 min), 20 min (±0.5 min), 40 min (±1 min), 1 h (±1 min), 1.5 h (±1.5 min), 2 h (±1.5 min), 3 h (±3 min), 4 h (±3 min), 6 h (±6 min), 8 h (±6 min), 12 h (±12 min), and 24 h (±36 min) post-dose on D28; for blood collection points of the 100 mg, 150 mg and 200 mg (alternative) groups, 72 h (±1 h, D31), 168 h (±2 h, D35), 240 h (±2 h, D38), and 312 h (±2 h, D41) post-dose on D28 are added
 - The PK blood sample collection will be listed

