	
randomized/enrolled subjects will be summarized. The number and percentage of subjects included in different analysis data sets will be calculated for each dose group.
 
Statistical Analysis of C-QTC Study:
 
Exploratory statistical analysis will be performed on C-QTc based on PK and QT interval changes. Descriptive analysis will be performed for QT/QTc intervals and changes from baseline at each time point, and line charts will be used to depict the changes at each time point and between groups. Baseline correction (<math>\Delta</math>QTc) and placebo correction (<math>\Delta\Delta</math>QTc) will be applied to the obtained QT/QTc intervals, with <math>\Delta</math>QTc as the dependent variable to measure the degree of drug effect on QT/QTc. The changes in drug concentration and QT/QTc intervals will be considered for model-based exploratory analysis.
 
Tolerability and Safety Evaluation:
 
Statistical analysis will be performed using SAS (v9.4 or above).
 
Adverse events (AEs) will be coded as per the Medical Dictionary for Regulatory Activities (MedDRA). The AEs observed during the trial will be described by system organ class (SOC) and preferred term (PT) for each dose group. Descriptive statistics of clinical laboratory tests, 12-lead ECGs, C-QTc study, vital signs, and physical examination results will be performed for each dose group. Clinically significant changes in clinical laboratory findings from baseline will be presented in the shift table.
 
Evaluation of the C-QTc study: The threshold of concern is a <math>\Delta\Delta</math>QTc interval prolongation exceeding 5 ms. Based on the C-QTc study results, it can be confirmed whether the conditions for conducting a TQT study are met. According to the C-QTc model, if the upper limit of two-sided 90% CI for <math>\Delta\Delta</math>QTcF corresponding to the highest clinical exposure is <math>\leq</math> 10 ms, it can be considered that the mean QT/QTc effect of the drug is not more than 5 ms, and the C-QTc study result is negative. However, if the upper limit of two-sided 90% CI for <math>\Delta\Delta</math>QTcF corresponding to low clinical exposure is <math>></math> 10 ms by model calculation, the C-QTc study result will be positive. When the upper limit of two-sided 90% CI for <math>\Delta\Delta</math>QTcF corresponding to low clinical exposure is <math>\leq</math> 10 ms and the upper limit of two-sided 90% CI for <math>\Delta\Delta</math>QTcF corresponding to the highest clinical exposure is <math>></math> 10 ms, the dose range for negative <math>\Delta\Delta</math>QTcF (<math>\leq</math> 10 ms) can be obtained with the model.
 
Pharmacokinetic Analysis:
 
Plasma concentrations will be summarized by dose group and scheduled sampling time point, including the number of subjects, the number of subjects below the quantification limit (BQL), arithmetic mean, standard deviation, coefficient of variation, median, minimum, maximum, geometric mean, and geometric coefficient of variation. Individual and mean plasma concentration-time (C-T) curves will be plotted separately.
 
Based on the non-compartmental model, Phoenix WinNonlin software (Certara USA Inc, version 8.2 or above) will be used to calculate PK parameters (main PK parameters include <math>T_{max}</math>, <math>C_{max}</math>, and AUC). PK parameters will be summarized by dose group, including the number of subjects, arithmetic mean, standard deviation, median, minimum, and

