6.5.7. QTc Analysis

Based on SS, QTc interval of subjects, changes from baseline (Δ QTc), and changes from

placebo ($\Delta\Delta QTc$) will be descriptively analyzed by dose group and visit time point, with the

mean value of the results at 3 time points before the first dose as the baseline.

• Visit time points include baseline, 1 h, 1.5 h, 2 h, 3 h, 4 h, 8 h, 12 h and 24 h post-

dose on D28

• In case of an explorative study, $\triangle QTc$ and drug concentration will be exploratively

analyzed using a linear mixed-effects model or Emax model (see the explorative statistical

analysis report of the First Bethune Hospital of Jilin University).

• The QTc interval will be classified and analyzed as $480 \ge QTc > 450$, $500 \ge QTc >$

480 and QTc > 500, and the change from baseline in QTc interval will be classified and

analyzed as $60 > \Delta QTc \ge 30$ and $\Delta QTc \ge 60$

7. Statistical Analysis Chart Template

See Attachment: BGT-002-004 SAP mockshell

16 / 16

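### Does SAP 6.4.1 need changing because it lists no BQL count and handles early BQL values differently in the concentration table and the curve?

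*SAP*

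**What the plan says.** Four places bear on the point.

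- **Protocol synopsis, Statistical Analysis, Pharmacokinetic Analysis.** Concentrations are summarised by dose group and scheduled time. The statistics named include "the number of subjects below the quantification limit (BQL".
- **SAP 6.4.1, list of statistics.** The same table is described by "planned blood collection time point, with the number of subjects, mean, standard deviation, geometric mean, median, quartiles, maximum, minimum, coefficient of variation" and geometric CV. A BQL count is not among them.
- **SAP 6.4.1, first two bullets.** In the table, BQL values will "be treated as missing values, and concentration data beyond the window will not be included in the descriptive analysis of plasma concentration". The second bullet begins with the mean curve, which "will be plotted according to the planned blood collection time", goes on to individual curves at actual times, and ends with a BQL rule: "those before reaching C_{max} will be treated as 0, while those after reaching C_{max} will be treated as missing values". SAP 6.4.2 repeats that rule for the PK parameters.
- **SAP 6.2.2.** "All data will be based on available observational data, and missing data will not be imputed".

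Two further items matter for traceability. SAP 6.4.1 ends with "The PK blood sample collection will be listed", and SAP section 7 refers to table shells ("See Attachment: BGT-002-004 SAP mockshell") that are not among the documents.

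**The concern.** Two things look wrong.

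First, the SAP appears to drop an output that the protocol names. Once BQL values become missing and nothing is imputed, a BQL subject simply leaves n. A fall from 9 to 6 could then mean three BQL results, three missed samples or three samples outside the window, and the table would not say which. The remaining mean would rest only on subjects with measurable drug and could be too high.

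Second, two BQL rules stand next to each other. If the zero rule covers the mean curve, one mean at one planned time has two values: the table would be empty at Day 1 pre-dose while the curve shows 0. At any early post-dose time with some BQL values, the curve would lie below the table.

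At stake is whether the descriptive concentration output can be read correctly. No hypothesis test or PK parameter is involved.

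**Working it through.** The plan gives no figure to reproduce. The check compares the rules and then asks how large a difference they could make.

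**1. Where the rules differ.**

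| Output | BQL before Cmax | BQL after Cmax |
|---|---|---|
| Table (6.4.1) | missing | missing |
| Individual curves (6.4.1) | 0 | missing |
| Mean curve (6.4.1) | 0, or missing as in the table, depending on reading | missing |
| PK parameters (6.4.2) | 0 | missing |

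The rules can conflict only before Cmax. The absent count is a separate matter and applies at every time point.

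**2. Size of a table-curve difference, if the curve uses zeros.** There are 9 active subjects per dose group (SAP 3.2), of whom k are assumed BQL. The table mean is S/(9-k) and the curve mean is S/9, where S is the sum of the quantifiable values. The ratio is 9/(9-k):

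- k = 1: 9/8 = 1.125
- k = 2: 9/7 = 1.286
- k = 3: 9/6 = 1.500
- k = 9 (expected at Day 1 pre-dose): table empty, curve 0

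**3. Is early BQL likely for the parent drug?** Inputs are the fasted values of the 100 mg food-effect trial in the protocol synopsis: Tmax 1.50 h, Cmax 16.64 µg/mL, half-life 41.07 h. I assume one compartment with first-order absorption and no lag.

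- ke = ln 2/41.07 = 0.0169 per h.
- ka solves ln(ka/ke)/(ka - ke) = 1.50 h, giving ka = 3.59 per h.
- C(t) = 16.64 × [exp(-ke·t) - exp(-ka·t)] / [exp(-1.5ke) - exp(-1.5ka)], which is 7.67, 11.87 and 15.39 µg/mL at 10, 20 and 40 min.

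A typical subject would be BQL at 10 min only with a lag of at least 10 min, and at 20 min only with a lag of at least 20 min. So 3 of the 13 Day 1 times (pre-dose, 10 and 20 min) are candidates, and only pre-dose is expected to be affected. On Day 28, with single-dose half-lives of 25.0 to 75.1 h, the fraction left 24 h after the previous dose is 2^(-24/25.0) = 0.51 to 2^(-24/75.1) = 0.80, so BQL before Cmax is implausible.

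**4. Late samples.** At 312 h after the last dose (100 mg and above), the fraction left is 2^(-312/25.0) = 0.02% to 2^(-312/75.1) = 5.6%. BQL is possible there, depending on a quantification limit that the documents do not give. All the rules treat such values as missing, so only the count is relevant.

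**5. Would zeros in the table be better?** It depends on why a value is BQL. If absorption has not started, the true value is 0, the zero rule is exact and the missing rule overstates the mean by the ratios in step 2. If the value is low but not zero, I simulated 200,000 groups of 9 lognormal values with the k lowest BQL:

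| Lognormal CV, k | Mean, missing rule | Mean, zero rule | Average sample CV: true / zero / missing |
|---|---|---|---|
| 50%, k = 1 | +6.7% | -5.1% | 0.46 / 0.58 / 0.41 |
| 50%, k = 3 | about +21% | -19.4% | 0.46 / 0.86 / 0.34 |
| 100%, k = 3 | +32.5% | -11.7% | 0.80 / 1.05 / 0.60 |

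For low non-zero values the zero rule gives a smaller error in the mean, though at CV 50% and k = 3 the two errors are nearly equal and opposite. It moves the CV further from truth in all three rows. It also makes the geometric mean, which both documents require, incalculable on the full set of values.

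**The case for a change.** The strongest case for a change is short. The protocol names the count and the SAP leaves it out; deferring detailed methods to the SAP does not explain dropping a named output. The unseen shells may carry a BQL row, but the SAP text does not ask for one. The sample listing allows tracing but is not a per-time-point summary. The gap also reaches the 72 to 312 h samples, where BQL may be more plausible than at 10 or 20 min, and the metabolites, for which no concentrations are given. The repair would be one column and one sentence.

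The textual omission stands, and so does its reach over all time points. What does not follow is that the plan must be altered. The protocol requirement is still in force and the SAP says nothing against it, so a programmer working from both documents has what is needed. If the count were still left out, the sample listing should show which subjects had on-time samples; any of these absent from n would be BQL, apart from failed assays.

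On the curve, two readings are open. The bullet opens with the mean curve, which favours applying the zero rule to it. The rule itself directly follows the description of individual curves, and being before Cmax is a property of one subject's profile, which favours confining it to those. On the second reading table and mean curve agree. The different rule in 6.4.2 is not a defect: a pre-dose zero anchors the AUC, while a table with a geometric mean cannot use zeros.

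**Conclusion.** No change follows. The missing count is a gap in the SAP text that the protocol already fills, and printing it alters no PK conclusion. The curve rule is ambiguous, but its only expected consequence is an empty cell against a plotted 0 at Day 1 pre-dose, which misleads nobody. A difference of 12.5% to 50% between table and curve needs one to three of nine subjects BQL after dosing and before Cmax, together with the reading that puts zeros on the mean curve. Nothing in the documents shows that this will occur. Imposing zeros on the table is a trade-off with no clear gain.

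This rests on three assumptions: that the analysts follow the protocol's list of statistics as well as the SAP's; that fasted absorption in these patients resembles that in healthy subjects at 100 mg; and that metabolite concentrations, on which the documents give no figures, are read only descriptively. The PK parameters and the dose-proportionality assessment are unaffected in any case, because they use the rule in SAP 6.4.2.
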